**Table 3-4 Objective Response Rate per RECIST 1.0 in Non-small Cell Lung Cancer Subjects (CA209003)**

Dose (mg/kg)	N	Histology	ORR No. of Subjects (%)	95% CI of ORR
1.0	15	SQ	0	0
	18	NSQ	1 (6)	0.1 - 27
3.0	18	SQ	4 (22)	6 - 48
	19	NSQ	5 (26)	9 - 51
10.0	21	SQ	5 (24)	8 - 47
	37	NSQ	7 (19)	8 - 35

CI: confidence interval, NSQ: non-squamous, ORR: objective response rate; SQ: squamous

## **4 ANALYSIS SETS**

The “Full Analysis Set (FAS)” will be the primary analysis set to be used in the efficacy endpoint evaluation.

The analysis set for the safety endpoint evaluation will be the “Safety Analysis Set (SAF)”.

The analysis set for the evaluation of the production of anti-ONO-4538 antibodies will be the “Anti-drug Antibody Analysis Set (ADAS)”.

### **4.1 Definitions of Groups**

Definitions of the individual groups are shown below.

#### **1) Enrolled Set (ENR)**

This set will be defined as group of subjects who have been enrolled.

#### **2) SAF**

This set will be defined as group of subjects who are included in ENR and have received at least one dose of the study drug.

#### **3) FAS**

This set will be defined as a full group of subjects who are included in SAF.

#### **4) ADAS**

This set will be defined as a group of subjects included in SAF and for whom the anti-ONO-4538 antibody level was determined once at baseline and at least once after the start of the study treatment.

### **4.2 Criteria for Subject Handling**

Details of subject handling are shown below.

#### **1) Subject without Administration**

Subject without Administration will be defined as those who have never administered the investigational product.

#### **2) Subjects with Incomplete Anti-drug Antibody Data**

Subjects with incomplete anti-drug antibody data will be defined as those for whom a baseline level of anti-ONO-4538 antibodies was not determined or for whom the levels of anti-ONO-4538 antibodies were never determined after the start of the study treatment.

How to handle subjects with other unexpected problems in the analyses will be decided by the sponsor before data lock through discussions about the details with the medical expert.

#### 4.3 Criteria for Handling Evaluation Time Points

If the actual date of examination is not the protocol-specified date of examination, the examination data will be accepted, except for those from diagnostic imaging, only when they are measured within the following criteria. To count days of the treatment period, the day of the start of each cycle will be defined as Day 1. If multiple data are present within the time window of a given time point, data which are obtained at a time point nearest the specified timing of examination will be preferred. If multiple safety data are obtained before and after the specified date and the lengths of time from the specified date and time are identical, those obtained after the specified date and time will be preferred.

##### 1. Treatment Period

Item	Treatment period					
	Cycle 1, Cycles 2 and beyond					
Trial day	1		8 b)	15 c)	29 c)	43
	Before dosing a)	After dosing b)				
Time window (days)	1		5 - 11	12 - 22	23 - 36	37 - 50

- a) In Cycle 1, Performance Status and laboratory test results which have been obtained within seven days before enrollment will be accepted. In Cycle 2 and subsequent cycles, the following data will be accepted: for vital signs, those within 1 day before administration, and for the other examinations, those within seven days before administration.
- b) Will only apply to Cycle 1.
- c) Data before administration will be accepted, except for serum drug concentrations.

##### 2. Post-treatment Follow-up Period (subjects who have terminated the treatment period)

Item	End of treatment period	Post-treatment follow-up period	
		Discontinuation at or within 28 days after the final dose	Follow-up
Time window (days)	-3 - +3	-7 - +7	-

## 5 DOCUMENTATION OF STATISTICAL METHOD

### 5.1 Efficacy Endpoints

#### 5.1.1 Primary Endpoint

1. Response rate (centrally assessed)

The response rate is the percentage of subjects given a best overall response assessment of CR or PR by the central imaging analysis facility.

In the overall response order of CR > PR > SD > PD > NE, the following criteria will be used to assess the best overall response from the overall response assessments made to the completion of the study. When the definitions of more than one response category are satisfied, the better of the two will be selected as the best overall response according to the order of CR > PR > SD > PD > NE.

- CR: Assessment of CR at least 2 consecutive times in intervals of 4 weeks (28 days) or longer.
- PR: Assessment of PR or greater (CR or PR) at least 2 consecutive times in intervals of 4 weeks (28 days) or longer.
- SD: The best overall response is neither CR nor PR but no overall response of PD is assessed 6 or more weeks after the start of treatment and at least one overall response of SD or better is assessed.
- PD: The best overall response is not CR, PR, or SD, and the overall response is PD.
- NE: The best overall response, which is not CR, PR, SD, or PD, is not evaluable.
- Without target lesions: there is target lesion in investigator assessment but not in central assessment.

The following overall responses will not be used to assess the best overall response:

- Overall response following the start or the end of follow-up of a subsequent NSCLC therapy
- Overall responses after an assessment of PD is made

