6. Unless medically necessary, vital signs will be measured no sooner than 2 days, and other tests will be performed no sooner than 8 days after the previous measurement.
7. Perform before administering the investigational product.
8. Other than weight.
9. Perform only in Cycle 4.
10. Perform only in Cycles 2, 4, 5, 7, and 9.
11. Perform only in Cycle 3.
12. Collect sample immediately before the completion of investigational product administration.
13. Perform every cycle (every 6 weeks) between Cycle 2 and 29 and every 2 cycles (every 12 weeks) after Cycle 30.

Table 4-3 Study schedule (for subjects completing the treatment phase)

Category	Study day	At end of treatment phase ⁶	Follow-up phase	
			28 days after final dose or on discontinuation 28 or fewer days after final dose ⁶	Follow-up ⁷
Allowable range (days)		-3 to +3	-7 to +7	-
Visit		V f-0	V f-1	V f-n
Pregnancy test ¹		○ ⁸	○	
Performance Status		○	○	
Vital signs/weight/percutaneous oxygen saturation		○	○	
Chest X-ray		○	○	
12-lead ECG		○ ⁸	○	
Hematology tests, blood biochemistry tests, urinalysis		○	○	
Immunology/hormone tests		○	○	
Serum drug concentration ²		○ ⁸	○	
Anti-ONO-4538 antibody ²		○ ⁸	○	
Diagnostic imaging (e.g., CT, MRI)		○	○	○
[REDACTED]	[REDACTED]	[REDACTED]	[REDACTED]	
	[REDACTED]	[REDACTED]	[REDACTED]	
	[REDACTED]	[REDACTED]	[REDACTED]	
Concomitant drugs/adverse events ⁵		←	→	

1. Women of childbearing potential will undergo urine pregnancy testing.
2. Perform only if the subject proceeds to the follow-up phase within 1 year after the start of investigational product administration (by Cycle 9). Collect sample if possible 6 to 12 weeks after the final investigational product dose.
[REDACTED]
[REDACTED]
5. Investigate all adverse events and concomitant treatments to the completion of the final tests (other than the survey for 'determination of outcome') specified in the protocol. Beyond the completion of the final tests (other than the survey for 'determination of outcome') specified in the protocol, follow any persisting adverse event for which a causal relationship with the investigational product cannot be ruled out, adverse events that resulted in discontinuation, and the concomitant treatments associated with those events until the events resolve, improve, or are determined to be permanent or no further follow-up is necessary. And all treatment-related adverse events will be followed every 2 weeks if possible.

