### 3.3.2 Treatment Phase

ONO-4538 will be administered every 2 weeks, to 3 times in total, with diagnostic imaging performed at Week 6. This constitutes one cycle. Subjects who satisfy all initiation criteria for the subsequent investigational product course and none of the investigational product discontinuation criteria may repeat this cycle. The study schedule for the treatment phase is shown in [Table 3-1](#) and [Table 3-2](#).

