**Table 3-1 Study schedule (Cycle 1)**

Category	Study day	Screening phase	Treatment phase (Cycle 1)					43 
			1		8	15	29	
			Before administration	After administration				
Allowable range (days)	-7 to -1		1		±3	-3 to +7	-6 to +7	-6 to +7
Visit	V 1-0		V 1-1		V 1-2	V 1-3	V 1-4	V 1-5
Written informed consent	○ 							
Demographics and inclusion/exclusion criteria	○							
Investigational product administration 			○			○	○	
Virus tests	○ 							
Pregnancy test 	○ 	○						
Performance Status	○ 				○	○ 	○ 	○
Vital signs/weight/percutaneous oxygen saturation	○ 	○ 	○ 		○ 	○ 	○ 	○
Chest X-ray 	○ 							○
12-lead ECG	○ 	○	○ 					○
Hematology tests, blood biochemistry tests, urinalysis	○ 				○	○ 		○
Immunology/hormone tests	○ 							○
Serum drug concentration		○	○ 			○ 	○ 	
Anti-ONO-4538 antibody		○				○ 	○ 	
		■						■
		■						■
		■						■
Diagnostic imaging (e.g., CT, MRI)	○ 							○
Concomitant drugs /adverse events				↔				↔

1. Administer the investigational product after at least 10 days have passed since the most recent dose.
2. Women of childbearing potential will undergo a serum pregnancy test in the screening phase and subsequently undergo urine pregnancy testing.
3. Also perform at unscheduled visits as necessary if, during the study (from the time of informed consent to the completion of the final tests (other than the survey for ‘determination of outcome’) specified in the protocol), signs, subjective and objective symptoms, or test findings suggest respiratory disease.

[REDACTED]

[REDACTED]

[REDACTED]

[REDACTED]

[REDACTED]

6. For subjects again proceeding to the treatment phase, administer the investigational product on Day 1 of the next cycle within the Day 43 allowable range (i.e., Days 37 to 50). Proceed to the follow-up phase (Table 3-3) on completing the treatment phase.
7. Begin administering the investigational product within 30 days of informed consent.

8. The data from virus tests performed within 1 year of enrollment, diagnostic imaging (e.g., CT, MRI) performed within 14 days of enrollment, and other tests performed within 7 days of enrollment will be included.

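### The 6-week condition in the SAP's stable-disease criterion (5.1.1) runs the wrong way: read literally, stable disease followed by imaging progression at or after week 6 is classed as PD

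*SAP*

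**What the plan says.** SAP 5.1.1 sets out the criteria for best overall response. For a subject who is not a confirmed CR or PR, SD has two conditions. The first is that "no overall response of PD is assessed 6 or more weeks after the start of treatment". The second is that some scan was read as SD or higher. No minimum time is attached to the SD assessment.

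Three other rules in the same section bear on this:

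- **Ordering:** "When the definitions of more than one response category are satisfied, the better of the two will be selected as the best overall response", with SD ranked above PD.
- **PD as the residual category:** "PD: The best overall response is not CR, PR, or SD, and the overall response is PD".
- **Responses not used:** these include "Overall responses after an assessment of PD is made". The first PD itself is still used.

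On timing, SAP 3.3.2 describes each cycle "with diagnostic imaging performed at Week 6". The Day 43 visit has a window: the next cycle starts "within the Day 43 allowable range (i.e., Days 37 to 50"). Protocol Table 4-2, footnote 13, continues imaging: "Perform every cycle (every 6 weeks) between Cycle 2 and 29", then every 12 weeks. SAP 4.3 sets visit windows but leaves scans out of them: "the examination data will be accepted, except for those from diagnostic imaging, only when they are measured within the following criteria".

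SAP 5.1.2 lists best overall response, central and investigator, as a secondary endpoint. Item 6 of SAP 9.2.4 reports the percentage in each category, with Wilson 95% intervals for CR, PR and SD.

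**The concern.** A time condition on SD would be expected to stop a subject who progresses very early from being credited with disease control. This one does the opposite. It ignores progression before week 6 and disqualifies a subject who progresses at any time from week 6 onward, however long the disease was stable.

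Treatment normally continues until PD (Protocol section 5; SAP 3.4) and scans recur every 6 weeks. PD after stable disease will therefore usually fall at or after week 6. If the sentence is programmed literally, most subjects whose SD ends in imaging progression would be counted as PD, and their number grows as follow-up lengthens. The trial has no comparator arm in which a similar shift might offset this. The SD percentage and its interval would then mainly describe subjects who had SD and no counted progression.

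**Working it through.** The documents give no figure on this point, so there is none to reproduce. The check applies the rule literally to test sequences.

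**Inputs, SAP 5.1.1.** Responses after the first PD are dropped. CR and PR each need two consecutive assessments at least 28 days apart. SD and PD are as quoted. Week 6 is taken as at least 42 days after first dose, i.e. Day 43 or later with first dose on Day 1.

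**Scan days.** The nominal scan in cycle c falls on Day 42c + 1. Cycle 1 is Day 43, Cycle 2 Day 85, Cycle 3 Day 127, Cycle 28 Day 1177 and Cycle 29 Day 1219. Day 1219 is 1218/30.4375 = 40.0 months after first dose.

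**Classification.** Two natural repairs are shown beside the literal rule. A: no PD before week 6. B: SD or better at or after week 6, before any PD.

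| Sequence | As written | A | B |
|---|---|---|---|
| SD at 28 scans (Days 43–1177), PD Day 1219 | PD | SD | SD |
| SD Day 43, PD Day 85 | PD | SD | SD |
| Unconfirmed PR Day 43, PD Day 85 | PD | SD | SD |
| SD Day 20, PD Day 38 | SD | PD | PD |
| SD Day 38, PD Day 80 | PD | SD | PD |
| SD Days 43 and 85, no PD | SD | SD | SD |
| PD only, Day 43 | PD | PD | PD |
| PR Days 43 and 85, PD Day 127 | PR | PR | PR |

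The first three rows are the main error. The fourth needs two scans before week 6, and none is scheduled before the Day 43 visit. The fifth shows that the two repairs differ for a scan inside the permitted window.

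**Could another rule rescue SD?** The ordering rule needs two satisfied definitions, and here SD is not satisfied. The residual PD definition then takes the subject. Dropping later responses leaves the first PD in place. SAP section 16 gives code only for the Wilson interval and Kaplan-Meier.

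**Shift per reclassified subject.** 1/41 = 2.44 points (planned squamous, SAP 3.7.1), 1/52 = 1.92 (planned non-squamous, SAP 3.7.1), 1/96 = 1.04 (treated as of 27 February 2015, SAP 14.4).

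**Illustration with assumed SD shares.** With p the intended SD share and z = 1.96, the Wilson lower limit is

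[p + z²/(2n) − z√(p(1−p)/n + z²/(4n²))] / (1 + z²/n).

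For 10/41: (0.2439 + 0.0468 − 1.96 × √(0.00450 + 0.00057)) / 1.0937 = 13.8%. Moving 4 subjects leaves 6/41 = 14.6%, above the limit. Moving 5 leaves 5/41 = 12.2%, below it.

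| Intended SD (assumed) | Wilson lower limit | Fewest reclassified to fall below it |
|---|---|---|
| 10/41 = 24.4% | 13.8% | 5 |
| 16/41 = 39.0% | 25.7% | 6 |
| 20/41 = 48.8% | 34.3% | 6 |
| 13/52 = 25.0% | 15.2% | 6 |
| 21/52 = 40.4% | 28.2% | 7 |
| 26/52 = 50.0% | 36.9% | 7 |
| 24/96 = 25.0% | 17.4% | 8 |
| 38/96 = 39.6% | 30.4% | 9 |
| 48/96 = 50.0% | 40.2% | 10 |

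**The case against.** The strongest reply is that the intent is recoverable. The variable is called a best response, SD ranks above PD, and SAP 9.1.3 and 9.2.3 tie assessment to RECIST 1.1. A sensible programmer might read the sentence as no PD until week 6. That reading is probably what was meant, but it does not settle the matter. The sentence says something else, the guideline is cited only in general terms, and the plausible repairs disagree on SD Day 38 then PD Day 80.

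A second reply is that SAP 9.1.3 and 9.2.3 describe the response as determined by the central facility or the investigator. If they supply the category themselves, no SAP program need apply this sentence. That stands as a limit: the harm is conditional on the text being applied. However, 5.1.1 says its own criteria will be used.

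Three further points also stand. Because PD is residual, the ordering rule never operates between SD and PD under any reading. The error therefore defeats the purpose of the ranking and is not a misuse of the rule. The Wilson limit is only a yardstick, since relabelling is not sampling error. And the reach is limited: SAP 9.2.1 calls the secondary analyses exploratory, and SAP 12.2 says no tests will be performed.

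**Conclusion.** The criterion is wrong as written and should be fixed. Applied literally, it moves every non-responder with SD or better followed by a counted imaging PD at or after week 6 from SD to PD. It also keeps as SD the rare subject with SD and then PD before week 6.

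The number reclassified is not in the documents. It ranges from none, if no stable subject later has a counted imaging PD, to all subjects intended as SD. The per-subject shifts follow from the documents' subject counts; the SD shares in the second table are assumptions.

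The damage is confined to the SD and PD percentages and the SD interval in the two best overall response tables. Both response rates, PFS, time to progression, duration of response, time to response and the sample size do not use the SD criterion. Subjects whose only assessment is PD, and PD seen after subsequent NSCLC therapy, are also unaffected. No conflict with RECIST 1.1 is claimed, because its SD rule is not printed in the documents.

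**What to change.** Replace the SD criterion in SAP 5.1.1 with wording such as: not CR or PR, and at least one overall response of SD or better, before any PD, at or after a stated minimum time from first dose. This is repair B in the working; if the sponsor intends repair A, it should say so explicitly.

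With the change:

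- State the minimum in days, once, so that 6 weeks and the Day 37–50 window agree. It has to be in 5.1.1, because 4.3 does not apply its windows to imaging.
- State the category for a subject whose only non-PD scans precede the minimum. A single SD on Day 20 with no PD is SD as written and under A, but NE under B.
- Check the wording against the RECIST 1.1 guideline cited in 9.1.3 and 9.2.3 and reconcile any difference.

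The cost is one SAP sentence and any derivation program that implements it. No new data are needed.

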#### 5.1.2 Secondary Endpoint

- 1 Response rate (investigator-assessed)
- 2 Overall survival
- 3 Progression free survival (centrally assessed and investigator-assessed)
- 4 Time to progression (centrally assessed)
- 5 Duration of response (centrally assessed)
- 6 Time to response (centrally assessed)

- 7 Best overall response (centrally assessed and investigator-assessed)
- 8 Percent change in tumor diameter of target lesion (investigator-assessed)

## **5.2 Safety Endpoints**

1 Adverse events

2 Laboratory tests

Hematology: RBC, MCV, MCH, MCHC, hemoglobin, hematocrit, WBC, differential WBC (neutrophils, lymphocytes, eosinophils, basophils, and monocytes) and platelet count

Blood biochemistry: Albumin, ALP, AST (GOT), ALT (GPT), total bilirubin, direct bilirubin,  $\gamma$ -GTP, total protein, creatinine, blood glucose, LDH, BUN, uric acid, CK (CPK), P, Ca, Na, K, and Cl

Qualitative urinalysis: Specific gravity, protein, glucose, occult blood, and sediment (WBC and RBC)

Immunology: Rheumatoid factor (RA), C-reactive protein (CRP), antinuclear antibody (ANA), SP-D, KL-6

Hormone tests: Thyroid-stimulating hormone (TSH), free triiodothyronine (free T3), and free thyroxine (free T4)

3 Vital signs (systolic blood pressure/diastolic blood pressure, pulse rate, body temperature), body weight, percutaneous oxygen saturation ( $SpO_2$ )

4 12-lead ECG

5 Chest X-ray

6 Performance Status (ECOG)

## **5.3 Other Endpoints**

### **5.3.1 Anti-drug Antibody Endpoint**

1 Anti-ONO-4538 antibody

## **6 DISPOSITION AND PROTOCOL DEVIATIONS**

### **6.1 Analysis Set**

Analysis will be performed in SAF. With regard to the analysis item (1) in [6.2 Analysis Items and Data Handling](#), the ENR will be the analysis set.

### **6.2 Analysis Items and Data Handling**

#### 1) Analysis Items

- (1) Reason for exclusion from the analysis set
- (2) Reason for termination of the treatment period
- (3) Reason for discontinuation or dropout of the clinical trial
- (4) Participants in the clinical trial per institution

#### 2) Data Handling

There will be no special handling.

### **6.3 Analysis Methods**

- 1) The analysis results will be summarized by squamous NSCLC and non-squamous NSCLC separately and totality.
- 2) Classification of subjects will be indicated according to subject criteria.
- 3) Frequency of subjects who have terminated the treatment period and frequency by reason for termination will be summarized.
- 4) Frequency of subjects who have discontinued and dropped out of the clinical trial and frequency by reason for discontinuation and drop out will be summarized.
- 5) Frequency of participants in the clinical trial per institution will be summarized.

## 7 STUDY DRUG EXPOSURE AND COMPLIANCE

### 7.1 Analysis Set

Analysis will be performed in SAF.

### 7.2 Analysis Items and Data Handling

#### 1) Analysis Items

- (1) Number of doses
- (2) Number of cycles
- (3) Duration of treatment (days)
- (4) Total dose (mg/kg)
- (5) Relative dose intensity (%)

#### 2) Data Handling

- (1) The number of doses will be the count of doses at all time points.
- (2) The number of cycles will refer to all cycles started, including those discontinued or temporarily suspended.
- (3) The duration of treatment will be calculated using the following formula.
  - Duration of treatment (days) = (the final dose date of investigational product) – (the first dose date of investigational product) + 1
- (4) The total dose (mg/kg) will be the sum of doses at all time points. The dose at each time point will be calculated using the following formula.
  - Dose at each time point (mg/kg) = (actual dose [mg]) / (body weight immediately before dosing [kg])
- (5) The relative dose intensity will be calculated using the following formula.
  - Relative dose intensity (%) = total dose (mg/kg) / {(the final dose date of investigational product – the first dose date of investigational product + 14[days]) × 3 (mg/kg)/14 (days)} × 100

### 7.3 Analysis Methods

- 1) The analysis results will be summarized by squamous NSCLC and non-squamous NSCLC separately and totality.
- 2) Frequency distribution and summary statistics of the number of doses will be calculated.
- 3) Frequency distribution and summary statistics of the number of cycles will be calculated.

- 4) Frequency distribution and summary statistics of the duration of treatment will be calculated.
- 5) Summary statistics of the total dose will be calculated.
- 6) Frequency distribution and summary statistics of the relative dose intensity will be calculated.

## 8 DEMOGRAPHIC AND BASELINE CHARACTERISTICS

### 8.1 Analysis Set

Analysis will be performed in SAF.

### 8.2 Analysis Items and Data Handling

#### 1) Background Factors

##### (1) Demographic Variables:

Sex, age, height, weight, and body mass index (BMI).

##### (2) Patient Characteristics:

Time from diagnosis date of primary disease to first dose date of the investigational product, histologic type, location of initial occurrence, TNM classification (baseline), metastasis lesions and stage (baseline), past medical history, concurrent diseases, NSCLC treatment history (surgical history, radiotherapy history, medication history, others, number of treatment regimens), drinking history, smoking history, performance status (ECOG).

